10.5.2 Young Mania Rating Scale (YMRS)

Descriptive statistics (n, mean, SD, minimum, median, and maximum) for YMRS assessments and changes from baseline values at each assessment visit and at the end of the DBTP will be presented by treatment group.

10.5.3 Abnormal Involuntary Movement Scale (AIMS)

Descriptive statistics (n, mean, SD, minimum, median, and maximum) for AIMS assessments and changes from baseline values at each assessment visit and at the end of the DBTP will be presented by treatment group.

10.5.4 Barnes Akathisia Rating Scale (BARS)

Descriptive statistics (n, mean, SD, minimum, median, and maximum) for BARS assessments and changes from baseline values at each assessment visit and at the end of the DBTP will be presented by treatment group.

10.5.5 Simpson Angus Scale (SAS)

[figure not shown]
Descriptive statistics (n, mean, SD, minimum, median, and maximum) for SAS assessments and changes from baseline values at each assessment visit and at the end of the DBTP will be presented by treatment group.

11. INTERIM ANALYSIS

No interim analysis is planned for this study.

12. SAMPLE SIZE CONSIDERATION

The sample size for this study is based on assumed effect size (treatment group difference relative to SD) of 0.37. This assumed effect size of 0.37 for lumateperone is based on a treatment difference of 3.3 units with a common pooled SD of 9 for the primary efficacy parameter, change from baseline to Day 43 in MADRS total score. A sample size of 350 patients (175 per treatment group) will be needed to be enrolled after Protocol Amendment 2.0 to provide 90% statistical power for primary analysis based on an MMRM using a simulation method (Lu 2012). The simulation assumed a correlation of 0.7 between the repeated measures and a dropout rate of 10% based on historical data.

13. STATISTICAL SOFTWARE

Statistical analyses of efficacy and safety parameters will be performed using version 9.4 of SAS.

14. DATA HANDLING CONVENTIONS

14.1 Visit Time Windows

Table 14-1 presents the visits assigned for efficacy and safety analyses and the corresponding range of treatment days (window) during which an actual visit may occur.

Derived Visit	Scheduled Visit (Day ^a)	Window ^b
Baseline	Week 0 (Day 1)	Days ≤ 1
Week 1	Week 1 (Day 8)	Days [2, 11]
Week 2	Week 2 (Day 15)	Days [12, 18]
Week 3	Week 3 (Day 22)	Days [19, 25]
Week 4	Week 4 (Day 29)	Days [26, 32]
Week 5	Week 5 (Day 36)	Days [33, 39]
Week 6	Week 6 (Day 43)	Days \geq 40 and within double-blind treatment period
End of Double-blind Treatment Period	Final or termination visit during the double-blind treatment period	
Week 8	Week 8 (Day 57)	Within the safety follow-up period

Table 14-1: Windows for Analysis Visits

a. Relative to the date of the first dose of double-blind study drug. For example, Day 1 = the date of the first dose of double-blind study drug.

b. Visit day is calculated as visit date – date of the first dose of double-blind study drug + 1 if the visit date is on or after the date of the first dose of double-blind study drug. Otherwise, it is calculated as visit date – date of the first dose of double-blind study drug.

If a patient has 2 or more non-missing assessment within the same window, the assessment closest to the target day will be used for analysis; if the 2 closet assessments are equidistant to the target day, the later one will be used for analysis.

14.2 Derived Efficacy Variables

The MADRS total score at a particular visit will be calculated using (sum of scores from nonmissing items) × (total number of items) / (number of non-missing items) only if the number of missing items is ≤ 2 . Otherwise, the MADRS total score will be set equal to missing.

14.3 Repeated or Unscheduled Assessments of Safety Parameters

If a patient has repeated assessments before the first dose of double-blind study drug, then the results from the final non-missing assessment made before the first dose of double-blind study drug will be used as baseline. If end-of-treatment assessments are repeated or if unscheduled visits occur, the last non-missing post-baseline assessment will be used as the end-of-treatment assessment for generating summary statistics. However, all post-baseline assessments will be used for PCS value determinations, and all assessments will be presented in the data listings.

14.4 Missing Date of the Last Dose of Study Drug

When the date of the last dose of double-blind study drug in the study is missing for a patient, all efforts should be made to obtain the date from the Investigator. If it is still missing after all efforts, then the last available dosing date in the DBTP will be used as the last dose date.

14.5 Missing Severity Assessment for Adverse Events

If severity is missing for an AE that occurred before the date of the first dose of double-blind study drug, then a severity of *mild* will be assigned. If the severity is missing for an AE that occurred on or after the date of the first dose of double-blind study drug, then a severity of *severe* will be assigned. The imputed values for severity will be used for the incidence summary; the actual values will be presented in data listings.

14.6 Missing Relationship to Study Drug for Adverse Events

If the relationship to study drug is missing for an AE that occurred after the date of the first dose of double-blind study drug, then a causality of Yes will be assigned. The imputed values for relationship to study drug will be used for the incidence summary; the actual values will be presented in data listings.

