9.4.6 Safety Analyses

All safety parameters will be summarized using the Safety Analysis Set as outlined in Table 9-1.

Safety data such as reported and observed AEs, treatment emergent AEs (TEAEs) and SAEs, clinical laboratory results, vital signs, physical examinations and neurological findings, ECGs, YMRS, AIMS, BARS, SAS, and C-SSRS) will be summarized by treatment group and by visit when appropriate. When appropriate, out-of-range values will be flagged in data listings and tabulated. Shift tables will be prepared for pre-specified safety measures, such as laboratory parameters and ECG. Parameters collected in duplicate or triplicate will be analyzed as an average of the measures for the relevant time point, including baseline.

Reported AE terms will be coded using the latest version of the Medical Dictionary for Regulatory Activities (MedDRA). TEAEs are defined as any AEs, regardless of the relationship to study drug, that occur or worsen in severity after the first dose of study medication and on or before the date of last dose of study medication plus one day. Treatment-related TEAEs will be defined as any TEAEs that are considered by the investigator to be either possibly, probably, or definitely related to study drug. If relationship to study drug is missing, the TEAE will be considered as treatment-related TEAEs, and SAEs will be summarized by treatment group, primary system organ class categories, and

preferred terms. If a patient reports the same TEAE more than once within the same system organ class and preferred term, the event with the worst-case relationship to study drug will be used in the corresponding relationship summaries. Similarly, if a patient reports a TEAE more than once within the same system organ class and preferred term, the event with the worst-case severity will be used in the corresponding severity summaries.

Patients who discontinue study or study drug due to AEs will be listed and summarized by system organ class and preferred term. TEAEs will be categorized to monitor signals of potential abuse of lumateperone and the number and percentage of patients with at least one abuse-related TEAE will be summarized by the pre-specified categories.

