10.1 Adverse Events

[figure not shown]
AEs will be coded using the Medical Dictionary for Regulatory Activities, version 20.1 or newer.

Treatment emergent AEs (TEAE) are defined as any AEs, regardless of the relationship to study drug, that occur or worsen in severity after the first dose of study drug and on or before the date of last dose of study drug plus one day. An event that occurs is referring to an event that did not occur before, or it started 2 days or more after the end date of the previous event for the same preferred term. Severity increases is referring to an increase in severity for a continuous event during the DBTP.

The number and percentage of patients reporting TEAEs in each treatment group will be tabulated by SOC and PT; by SOC, PT, and severity; and by SOC, PT, and relationship to study drug. If more than 1 AE is coded to the same PT for the same patient, the patient will be counted only once for that PT using the most severe and most related occurrence for the summarization by severity and by relationship to study drug, respectively.

The incidence of common (\geq 5% of patients in any treatment group) TEAEs will be summarized by PT and treatment group and sorted by decreasing frequency for the lumateperone 42 mg group.

The incidence of serious adverse events (SAEs) and of AEs leading to premature discontinuation of study drug will also be summarized by SOC, PT, and treatment group and will be sorted by decreasing frequency for lumateperone 42 mg group. Listings will be presented for patients with SAEs, patients with AEs leading to premature discontinuation of study drug, patients who died (if any) and patients who died (if any) with AEs.

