14.8 Missing Date Information for Adverse Events

The following imputation rules only apply to cases in which the start date for AEs is incomplete (i.e., partly missing).

Missing month and day

- If the year of the incomplete start date is the same as the year of the first dose of doubleblind study drug, the month and day of the first dose of double-blind study drug will be assigned to the missing fields
- If the year of the incomplete start date is before the year of the first dose of double-blind study drug, December 31 will be assigned to the missing fields
- If the year of the incomplete start date is after the year of the first dose of double-blind study drug, *January 1* will be assigned to the missing fields

Missing month only

• If only the month is missing, the day will be treated as missing and both the month and the day will be replaced according to the above procedure

Missing day only

- If the month and year of the incomplete start date are the same as the month and year of the first dose of double-blind study drug, the day of the first dose of double-blind study drug will be assigned to the missing day
- If either the year of the incomplete start date is before the year of the date of the first dose of double-blind study drug or if both years are the same but the month of the incomplete start date is before the month of the date of the first dose of double-blind study drug, the last day of the month will be assigned to the missing day
- If either the year of the incomplete start date is after the year of the date of the first dose of double-blind study drug or if both years are the same but the month of the incomplete start date is after the month of the date of the first dose of double-blind study drug, the first day of the month will be assigned to the missing day

If the stop date is complete and the imputed start date as above is after the stop date, the start date will be imputed by the stop date.

If the start date is completely missing and the stop date is complete, the following algorithm will be used to impute the start date:

- If the stop date is after the date of the first dose of double-blind study drug, the date of the first dose of double-blind study drug will be assigned to the missing start date
- If the stop date is before the date of the first dose of double-blind study drug, the stop date will be assigned to the missing start date

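### SAP 14.6 leaves first-dose-day TEAEs with a missing drug relationship outside its related-by-default rule, contrary to protocol 9.4.6

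*SAP*

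**What the plan says.** - **Missing relationship, SAP 14.6.** Causality is set to Yes under one condition: "If the relationship to study drug is missing for an AE that occurred after the date of the first dose of double-blind study drug". The section then states: "The imputed values for relationship to study drug will be used for the incidence summary". It gives no rule for events outside that condition.
- **Missing relationship, protocol 9.4.6.** "If relationship to study drug is missing, the TEAE will be considered as treatment-related". The rule is tied to the event being a TEAE, not to a calendar date.
- **TEAE window.** Protocol 9.4.6 covers events "that occur or worsen in severity after the first dose of study medication" and SAP 10.1 covers events "that occur or worsen in severity after the first dose of study drug". Both start the window at the dose itself. Protocol section 4 and SAP section 2 place that dose on the evening of Day 1.
- **Missing severity, SAP 14.5.** The neighbouring rule assigns severe under a wider condition: "If the severity is missing for an AE that occurred on or after the date of the first dose of double-blind study drug".
- **Incomplete start dates, SAP 14.8.** If the start date is wholly missing and the event stopped after the date of first dose, "the date of the first dose of double-blind study drug will be assigned to the missing start date". If only the day is missing and the month and year match those of the first dose, "the day of the first dose of double-blind study drug will be assigned to the missing day". A missing month, with or without the day, is handled in the same way when the year matches.
- **Departures from the protocol.** Protocol section 9 requires changes to its analysis methods to be documented in the SAP. SAP 15 reports none.

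**The concern.** The SAP condition is one calendar day narrower than the protocol rule. That day is the one on which the first dose is taken, in the evening, so an event later that night is a TEAE but carries the excluded date. SAP 14.8 adds to the group, because it moves several kinds of incompletely dated event onto the same date. Some of those events may really have begun later in treatment.

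What is at stake is the SAP 10.1 table of TEAEs by system organ class, preferred term and relationship. Compared with the protocol rule, its related counts could only be too low. A reader relying on SAP 15 would not know that the rule had changed.

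**Working it through.** The plan gives no figure to reproduce. The check applies the SAP rules to possible start dates.

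Let D be the date of first dose and S the start date of the event after any imputation under SAP 14.8. The two default rules are:

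- SAP 14.5, missing severity: assign severe if S ≥ D.
- SAP 14.6, missing relationship: assign Yes if S > D.

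They differ only at S = D, where D ≥ D is true and D > D is false. The question is which events have S = D. The SAP 14.8 rules were coded and run on 15 start-date and stop-date patterns with an arbitrary D. Five patterns land on D:

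| Start date as recorded | S under 14.8 | 14.5 applies | 14.6 applies |
|---|---|---|---|
| Complete, equal to D | D | yes | no |
| Day missing, month and year match D | D | yes | no |
| Month and day missing, year matches D | D | yes | no |
| Month only missing, year matches D | D | yes | no |
| Wholly missing, stop date after D | D | yes | no |

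The other ten patterns divide as follows:

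- Three land after D, and both rules apply.
- Five land before D, and neither rule applies. One of these is a start with the day missing in the first-dose month and a complete stop date before D; SAP 14.8 then moves the start to the stop date.
- Two receive no date, because SAP 14.8 has no rule for a wholly missing start when the stop date equals D or is also missing. That is a separate gap.

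Total: 5 + 3 + 5 + 2 = 15.

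Next, compare the S = D events with the protocol:

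1. A Day 1 event that starts after the evening dose is a TEAE. Protocol 9.4.6 counts it as related if the relationship is missing; SAP 14.6 does not impute it.
2. An event placed on D by SAP 14.8 and classed as a TEAE is in the same position.
3. A Day 1 event that starts before the dose is not a TEAE, and protocol 8.3.1.3.1 makes it unrelated by definition. There is no conflict for these events.

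The conflict is therefore confined to items 1 and 2, and within them to events whose relationship is missing.

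**The case against.** Several points can be made for the plan.

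- **SAP 14.6 is silent, not contrary.** It does not say that events outside its condition are unrelated. The SAP presents itself as an elaboration of the protocol and declares no changes, so protocol 9.4.6 might be read as filling the gap. This is a fair reading of intent, but the SAP still states a narrower condition, and a programmer who follows it literally will not impute these events.
- **The protocol sentence is damaged.** In the text as extracted, it runs into the next sentence, and a lost qualifier cannot be excluded. The rule itself is still legible.
- **Few events will qualify.** Protocol 8.3.1.5.1 requires a causality assessment for every event, and protocol 12.2 provides for completeness checks and queries before database lock. The rule matters only for what is still missing after that. This stands, and it limits the size of the point.

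A reader might also infer more than the documents support:

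- **That every first-dose-day event is wrongly left out.** Events before the evening dose are unrelated by definition.
- **That the severity and relationship tables would contradict each other.** An event would need both items missing for the two defaults to meet. Even then, severity and relationship are separate attributes shown in separate tables.
- **That the gap favours lumateperone.** Nothing in the documents gives a reason for it to fall unequally on two blinded arms.

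**Conclusion.** SAP 14.6 is wrong as written. Its literal condition is narrower than protocol 9.4.6 for TEAEs that start on Day 1 after the dose and for TEAEs whose start date SAP 14.8 sets to the first-dose date. The departure is not declared in SAP 15.

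The size cannot be computed, because the documents do not say how many events will have a missing relationship. It is probably very small. The table is descriptive, so no hypothesis test is affected.

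The conclusion rests on three assumptions: that SAP 14.6 is applied literally; that events outside its condition stay missing and so are not counted as related; and that events which SAP 14.8 places on the first-dose date are classed as TEAEs. The supplied text does not say how an event on that date is classed when no start time is known.

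**What to change.** Tie SAP 14.6 to TEAE status instead of the calendar date, for example: *A TEAE with no recorded relationship to study drug is assigned a causality of Yes.* This matches protocol 9.4.6 and, on this point, makes the statement in SAP 15 true.

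Copying the *on or after the date* condition from SAP 14.5 is the weaker choice. Taken alone, it would also assign Yes to Day 1 events that began before the dose, against protocol 8.3.1.3.1. The TEAE wording avoids this as far as pre-dose and post-dose events on Day 1 can be told apart. The supplied text does not say whether event start times are collected, so the SAP should also state how an untimed Day 1 event is classed.

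If the narrower condition is intended, SAP 15 should declare and justify it. The change is one sentence in the SAP plus the matching line of programming, and needs no new data. Relative to the literal SAP rule, related counts can only stay the same or rise slightly.

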14.7 Missing Dates Information for Adverse Events

The following imputation rules apply only to cases in which the start date is incomplete (i.e, partially missing) for AEs and prior/concomitant medications.

14.8 Missing Date Information for Adverse Events

The following imputation rules only apply to cases in which the start date for AEs is incomplete (i.e., partly missing).

Missing month and day

- If the year of the incomplete start date is the same as the year of the first dose of doubleblind study drug, the month and day of the first dose of double-blind study drug will be assigned to the missing fields
- If the year of the incomplete start date is before the year of the first dose of double-blind study drug, December 31 will be assigned to the missing fields
- If the year of the incomplete start date is after the year of the first dose of double-blind study drug, *January 1* will be assigned to the missing fields

Missing month only

• If only the month is missing, the day will be treated as missing and both the month and the day will be replaced according to the above procedure

Missing day only

- If the month and year of the incomplete start date are the same as the month and year of the first dose of double-blind study drug, the day of the first dose of double-blind study drug will be assigned to the missing day
- If either the year of the incomplete start date is before the year of the date of the first dose of double-blind study drug or if both years are the same but the month of the incomplete start date is before the month of the date of the first dose of double-blind study drug, the last day of the month will be assigned to the missing day
- If either the year of the incomplete start date is after the year of the date of the first dose of double-blind study drug or if both years are the same but the month of the incomplete start date is after the month of the date of the first dose of double-blind study drug, the first day of the month will be assigned to the missing day

If the stop date is complete and the imputed start date as above is after the stop date, the start date will be imputed by the stop date.

If the start date is completely missing and the stop date is complete, the following algorithm will be used to impute the start date:

- If the stop date is after the date of the first dose of double-blind study drug, the date of the first dose of double-blind study drug will be assigned to the missing start date
- If the stop date is before the date of the first dose of double-blind study drug, the stop date will be assigned to the missing start date

14.9 Missing Date Information for Prior or Concomitant Medications

For prior or concomitant medications, incomplete (ie, partly missing) start dates and/or stop dates will be imputed. When the start date and the stop date are both incomplete for a patient, the start date will be imputed first.

14.9.1 Incomplete Start Date

The following rules will be applied to impute the missing numeric fields for an incomplete prior or concomitant medication start date. If the stop date is complete (or imputed) and the imputed start date is after the stop date, the start date will be imputed using the stop date.

Missing month and day

- If the year of the incomplete start date is the same as the year of the first dose of doubleblind study drug, the month and day of the first dose of double-blind study drug will be assigned to the missing fields
- If the year of the incomplete start date is before the year of the first dose of double-blind study drug, *December 31* will be assigned to the missing fields
- If the year of the incomplete start date is after the year of the first dose of double-blind study drug, *January 1* will be assigned to the missing fields

Missing month only

• If only the month is missing, the day will be treated as missing and both the month and the day will be replaced according to the above procedure

Missing day only

- If the month and year of the incomplete start date are the same as the month and year of the first dose of double-blind study drug, the day of the first dose of double-blind study drug will be assigned to the missing day
- If either the year of the incomplete start date is before the year of the date of the first dose of double-blind study drug or if both years are the same but the month of the incomplete start date is before the month of the date of the first dose of double-blind study drug, the last day of the month will be assigned to the missing day.
- If either the year of the incomplete start date is after the year of the date of the first dose of double-blind study drug or if both years are the same but the month of the incomplete start date is after the month of the date of the first dose of double-blind study drug, the first day of the month will be assigned to the missing day

